9.2.2. Exclusion Criteria

There are no exclusion criteria for this study (ie, for either Objective 1 or Objective 2).

9.3. Variables

Please refer to Statistical Analysis Plan (SAP).

9.4. Data Sources

The CorEvitas RA Registry is an observational registry and therefore collects patient and physician data at patient clinical visits with the rheumatologist. Unlike clinical studies, visits are not timed at exact uniform time periods. Thus, time period definitions for the current study need to accommodate this unique feature of observational registries.

“Index visit” is defined as the visit when tofacitinib was initiated, ie, first ever use of tofacitinib. Only initiations at or after enrollment into the Registry are included.

A “6-month” follow-up is defined as a clinical visit to the rheumatologist 3 to 9 months from the enrollment visit in accordance with the Registry protocol.

Initiations between visits

If tofacitinib is initiated between visits, then baseline variables from the visit prior to the initiation of tofacitinib will be used, as long as the prior visit occurred within four months of the tofacitinib start date. Initiations that occur between visits and where the prior visit is greater than 4 months from the initiation will be excluded.

Multiple visits in the same time window

Given the observational nature of the data, it is possible for patients to have more than one visit that falls within a given follow-up period's allowed time window. For example, a patient might have a visit with outcomes collected at 5 months and then 9 months, both of which would qualify as a "6-month" visit. In that case, the latest visit will be chosen as the "6-month" follow-up since we would like to consider the longest follow-up possible. The exception to this rule is if values for the primary outcome are unavailable for the latest visit, in which case the first visit will be used instead.

Discontinuations prior to follow-up

For patients who discontinued tofacitinib prior to follow-up and who do not switch to another drug, the clinical or patient-reported outcome value at the follow-up visit will be used. If a patient discontinues and switches to another biologic/tsDMARD, the value at the switch visit, if available, will be used; otherwise, the value will be set to missing.

9.4.1. Exposure

The exposure of interest in this study is first ever tofacitinib use after any prior rituximab use. All patients in the study will be classified as exposed.

9.4.2. Study Outcomes

Objective 1: Characterize Patients at tofacitinib initiation

Primary Outcome:

- Objective 1 is to characterize patients at tofacitinib initiation. All variables as outlined in the SAP will be summarized for this aim.

Objective: Describe change in 6-month outcomes.

Primary Outcome:

- Change in CDAI.

Secondary Outcomes:

- Achievement of Minimum Clinically Important Difference (MCID):² (change in CDAI from baseline to follow-up = Δ CDAI).

CDAI at Index	MCID to Define Improvement in Disease Activity at FU Visit If ΔCDAI>MCID
Low: CDAI \leq 10	1
Moderate: 10 $>$ CDAI \leq 22	6
High $>$ 22	12

- Change in HAQ.
- Change in patient pain.
- Change in patient fatigue.
- Number (%) of tofacitinib discontinuations prior to or at 6-month visit.

9.5. Study Size

As of the 31 March 2021 data cut, there were 390 tofacitinib initiators with history of rituximab use. Of these:

- ~376 have baseline CDAI information.
- Line of therapy (and baseline CDAI) is available for ~373, of whom n=8 (2%) are 3rd line and n=365 (98%) are 4th line.
 - Note: since population is restricted to those with prior rituximab use, 3rd line use reflects patients with prior rituximab use only 4th line reflects patients with one or more prior biologic in addition to rituximab.
- ~107 have CDAI information at baseline and 6 months follow-up.

9.6. Data Management

All statistical analyses will be conducted using Stata Release 16 (StataCorp LLC, College Station TX) and/or R Version 4.0.3 (The R Foundation for Statistical Computing, Vienna Austria).

9.6.1. Case Report Form (CRFs)/Data Collection Tool (DCTs) Data Record

Not Applicable, however:

- All study data exist as structured data by the time of study start.
- The conversion of unstructured data to structured data during the implementation of the protocol is performed solely by a computer using automated/algorithmic methods, such as natural language processing.

9.6.2. Record Retention

Not Applicable, however:

To enable evaluations and/or inspections/audits from regulatory authorities or Pfizer, CorEvitas agrees to keep all study-related records. The records should be retained by CorEvitas according to local regulations or as specified in the vendor contract, whichever is longer. CorEvitas must ensure that the records continue to be stored securely for so long as they are retained.

9.7. Data Analysis

[figure not shown]
Detailed methodology for summary and statistical analyses of data collected in this study will be documented in the SAP, which will be dated, filed and maintained by the sponsor. The SAP may modify the plans outlined in the protocol; any major modifications of primary endpoint definitions or their analyses would be reflected in a protocol amendment.

9.8. Quality Control

Data quality is controlled, monitored, and managed according to the CorEvitas Master Registry Monitoring Plan (RMP). All study personnel must complete standardized protocol training prior to initiating data collection. Each Investigator is also required to designate one staff member as the primary Registry Coordinator responsible for addressing data clarifications requests from CorEvitas in a timely manner. All data collectors in the field have continuous access to a dedicated Registry Manager who answers questions and provides guidance on specific definitions and clinical situations.

Data quality review (ie, monitoring) occurs at the site level as well as in aggregate to check for Case Report Form completeness, consistency, and compliance with all data collection requirements set forth in the registry protocol. Monitoring is performed in addition to the edit checks and event completion rules configured in the 21 CFR Part 11 compliant EDC system. The majority of monitoring is conducted using centralized (ie, remote) methods in

PFIZER CONFIDENTIAL

accordance with the Agency for Healthcare and Research Quality's (AHRQ) data collection and quality assurance recommendations.³ These methods include but are not limited to routine remote monitoring visits and automated database quality control listings. Onsite audits of source data are also performed for a subset of registry sites as defined by the Master RMP.

Remote monitoring visits are conducted for the duration of the registry beginning when the first patient is enrolled. Qualified monitors within CorEvitas' Clinical Data Management (CDM) department are responsible for conducting remote monitoring visits. Registry Managers are responsible for site retraining and resolving any compliance issues identified during these visits. Sites also receive data clarification requests (ie, queries) at regular intervals from designated CDM and Pharmacovigilance personnel. Queries are issued and tracked through the study's EDC system. Sites are required to respond to data queries within 5 to 7 business days of receipt.

9.9. Limitations of the Research Methods

The CorEvitas RA Registry used in this research includes a sample of adults with RA that are not necessarily representative of all adults with RA in the US, or of those in emerging markets outside the United States (US). In particular, these are patients with RA with clinical visits with rheumatologists.

Most importantly for this study, in the US rituximab is typically prescribed as a later line therapy, after failure of one or more tumor necrosis factor inhibitor (TNFi). It is also given as a first-line bDMARD to patients with contraindications to tumor necrosis factor (TNF) inhibitors (eg, interstitial lung disease).⁴ This may differ from prescribing patterns in countries other than the US, which could influence the generalizability of the results to RA patients outside of the US.

In addition, history of medication use prior to enrollment is derived from what is reported by patients and their current rheumatologist within the registry. Since the registry is not based on an inception cohort, patients may not be able to recall their entire medication history, leading to possible mischaracterization regarding prior use of rituximab. The registry captures physician-reported prescribing, but there are no measures of patient adherence.

Confounding by indication can occur when factors that determine physicians' selection of a particular treatment (eg, disease severity, comorbidities) also affect the outcome being studied. There are certain conditions (tuberculosis [TB], lymphoma) that would prompt the prescribing of rituximab. This population could have different outcomes than a population without these comorbidity histories.

Patients who maintain treatment at 6 months may have different outcomes compared to the outcomes those who discontinue or switch would have had, had they not discontinued/switched. This study takes steps to mitigate this potential bias by including values at follow-up for those who discontinue treatment and values at switch for those who switch, as described above.

9.10. Other Aspects

9.10.1. Strengths

CorEvitas was founded in 2000 without any ownership links to the pharmaceutical industry. CorEvitas has a clear track record of published scientific research using the CorEvitas data to provide answers to clinically relevant questions in a real-world setting.

The CorEvitas RA Registry is a longitudinal prospective registry collecting data from both patients and providers on RA treatment and a wide range of both physician- and patient-reported disease outcomes. This provides a unique resource on the real-world use of biologic drugs in the US. The registry contains clinical data (eg, disease activity scores, comorbidities, patient-reported outcomes data, etc.) that are not available in claims databases.

9.11. CorEvitas Publication Policy

All analyses for the public domain are subject to the CorEvitas publication policy (please see the full policy for details; the policy is available upon request). Briefly, the policy describes our adherence to industry best practices for the development, conduct and reporting of research. For comparative studies (any study that assesses effectiveness, persistency, safety and other outcomes in >1 treatment group), analyses need to mitigate sources of systematic bias. In addition, safety studies cannot be performed where the analyses may undermine ongoing or recently completed regulatory commitments. Lastly, courtesy review is provided for comparative studies that impact subscribers including safety studies for subscribers with current or recently conducted regulatory commitments.

10. PROTECTION OF HUMAN SUBJECTS

10.1. Patient Information

This study involves data that exist in anonymized structured format and contain no patient personal information.

10.2. Patient Consent

As this study involves anonymized structured data, which according to applicable legal requirements do not contain data subject to privacy laws, obtaining informed consent from patients by Pfizer is not required.

10.3. Institutional Review Board (IRB)/Independent Ethics Committee (IEC)

This study does not contain any identifying patient information (eg, name) and is exempt from IRB review.

10.4. Ethical Conduct of the Study

The study will be conducted in accordance with legal and regulatory requirements, as well as with scientific purpose, value and rigor and follow generally accepted research practices described in Good Practices for Outcomes Research issued by the International Society for Pharmacoeconomics and Outcomes Research (ISPOR) and contained in the CT24-WI-GL02-RF04.

11. MANAGEMENT AND REPORTING OF ADVERSE EVENTS/ADVERSE REACTIONS

This study involves data that exist as structured data by the time of study start. In these data sources, individual patient data are not retrieved or validated, and it is not possible to link (ie, identify a potential association between) a particular product and medical event for any individual. Thus, the minimum criteria for reporting an adverse event (AE) (ie, identifiable patient, identifiable reporter, a suspect product, and event) cannot be met.

12. PLANS FOR DISSEMINATING AND COMMUNICATING STUDY RESULTS

[figure not shown]
For all publications relating to the Study, Pfizer will comply with recognized ethical standards concerning publications and authorship, including Section II - "Ethical Considerations in the Conduct and Reporting of Research" of the Uniform Requirements for Manuscripts Submitted to Biomedical Journals, <http://www.icmje.org/index.html#authorship>, established by the International Committee of Medical Journal Editors.

In the event of any prohibition or restriction imposed (eg, clinical hold) by an applicable competent authority in any area of the world, or if the party responsible for collecting data from the participant is aware of any new information which might influence the evaluation of the benefits and risks of a Pfizer product, Pfizer should be informed immediately.

14. LIST OF TABLES

Table shells are included in the SAP.

15. LIST OF FIGURES

Figures are included in the SAP.

16. ANNEX 1. LIST OF STAND ALONE DOCUMENTS

Not Applicable.

2. LIST OF ABBREVIATIONS

| | |
|-----------------|---|
| BMI | Body Mass Index |
| CABG | Coronary Artery Bypass Grafting |
| CDAI | Clinical Disease Activity Index |
| CDM | Clinical Data Management |
| CHF | Congestive Heart Failure |
| CI | Confidence Interval |
| csDMARD | Conventional Disease-Modifying Antirheumatic Drug |
| bDMARD | Biologic Disease-Modifying Antirheumatic Drug |
| DVT | Deep Venous Thrombosis |
| EQ-5D | Euro-QoL 5-Dimensional |
| ERB | Ethical Review Board |
| GPP | Good Pharmacoepidemiology Practices |
| HAQ | Health Assessment Questionnaire |
| IEC | Independent Ethics Committee |
| IQR | Interquartile Range |
| IRB | Institutional Review Board |
| MCID | Minimum Clinically Important Difference |
| MI | Myocardial Infarction |
| MTX | Methotrexate |
| PCI | Percutaneous Coronary Intervention |
| PGA | Physician Global Assessment |
| PII | Personally Identifiable Information |
| PRO | Patient Reported Outcome |
| RA | Rheumatoid Arthritis |
| RTX | Rituximab |
| SD | Standard Deviation |
| TIA | Transient Ischemic Attack |
| TNFi | Tumor Necrosis Factor inhibitors |
| Non-TNFi | Non-Tumor Necrosis Factor inhibitors |
| TOFA | Tofacitinib |
| VAS | Visual Analogue Scale |

3. AMENDMENTS AND UPDATES

| Amendment number | Date | Section(s) changed | Summary of the change(s) | Reason(s) for the change(s) |
|------------------|-------------|--------------------|---|--|
| 1 | 06-Jan-2023 | Title page | Updated study Team members and version date | |
| 1 | 06-Jan-2023 | 4.4.3.3. | 
Replaced sentence "For patients who discontinued tofacitinib prior to follow-up and who do not switch to another drug, the clinical or patient-reported outcome (listed in Section 4.4.5.2) value at the follow-up visit will be used. If a patient discontinues and switches to another biologic/tsDMARD, the value at the switch visit, if available, will be used; otherwise the value will be set to missing.
 
As a sensitivity analysis, we will employ the same approach to discontinuations as above, but in cases where a value for a clinical or patient-reported outcome is not available at switch (among patients who switch), we will impute non-response for all binary variables (listed in Section 4.4.5.2)" with "For patients who discontinue tofacitinib prior to 6 months window, the clinical or patient-reported outcome (listed in Section 4.4.5.2) will be imputed via last observation carried forward (LOCF), using only registry visits that occur before the discontinuation. Specifically, outcomes observed at a registry visit in the 6-month window will use data collected at that visit with the following exception.
 
Patients that discontinue tofacitinib at a registry visit prior to the six month window will have the outcomes collected at that registry visit carried forward as the outcomes in the 6-month window. A patient that discontinues tofacitinib between registry visits will have the outcomes collected at the registry visit prior to the discontinuation carried forward as the 6-month outcome."
 | CorEvitas has updated the general practices for handling discontinuations in effectiveness studies in real world settings. |
| 1 | 06-Jan-2023 | 4.4.7.2. | Aim 2 Sensitivity analysis has been removed | With the proposed changes a sensitivity analysis is not needed. |
| 2 | 04-May-2023 | 4.4.6.6. | Added line of therapy of RTX and year of RTX discontinuation | Data of last date of use of RTX requested by MSC team if available |

| | | | | |
|---|-------------|----------|--|--|
| 2 | 04-May-2023 | 4.4.7.2. | added sentence “A subgroup analysis related to the outcomes for Aim 2 will be carried out focused on patients who used rituximab immediately prior to tofacitinib”. | |
| 2 | 04-May-2023 | Table 1 | Added line of therapy of RTX and year of RTX discontinuation | Data of last date of use of RTX requested by MSC team if available |
| 2 | 04-May-2023 | Table 4 | Effectiveness outcomes were reported for the subgroup of those with 6-months follow-up and had used rituximab immediately prior to tofacitinib (see Table 4). | Data of last date of use of RTX requested by MSC team if available |

4. RESEARCH METHODS

4.1. Background and Rationale

Rheumatoid arthritis (RA) is a chronic, immune-mediated, inflammatory disease affecting many joints, including those in the hands and feet. RA has a wide global presence and is estimated to affect 0.5 to 1% of the general population.

Some authorities in emerging markets prioritize use of rituximab (RTX) in treatment of RA because of its relatively lower cost and availability in hospitals. Newer molecules (e.g., tofacitinib) usually do not have clinical trial data in RTX-experienced RA patients. There is a need to understand the use of and effectiveness of tofacitinib in the real-world, to provide information for healthcare providers in these emerging market settings.

4.2. Objectives

To characterize the use of tofacitinib after use of rituximab in patients with RA in a real-world setting.

4.2.1. Primary Objective(s)

Describe the characteristics of tofacitinib initiators with a history of rituximab exposure, at time of tofacitinib initiation

4.2.1.1. Hypotheses

This is a descriptive aim without an a priori hypothesis.

4.2.2. Secondary Objective(s)

Describe 6-month outcomes for tofacitinib initiators with a history of rituximab exposure

4.2.2.1. Hypotheses

This study is descriptive with no formal hypothesis, but it is anticipated that outcomes will improve over the 6-month time period.

4.2.3. Exploratory Objective(s)

There was initial interest in stratifying by history of tuberculosis and history of lymphoma at time of tofacitinib initiation. At this time, sample size is not feasible for either analysis ($n < 10$ for both TB and lymphoma), and so no exploratory objectives will be pursued.

4.3. Expected Results

The motivation for the study is to characterize patients who initiate tofacitinib and have a prior history of RTX in a real-world setting. The study will also provide evidence of the effectiveness of tofacitinib in the real world, in a population with prior rituximab experience.

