4.4.4. Exposure

The exposure of interest in this study is first ever tofacitinib use after any prior RTX use. All patients in the study will be classified as exposed.

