4.4.5.2. Aim 2: Describe change in 6-month outcomes

4.4.5.2.1. Primary Outcome:

- Change in Clinical Disease Activity Index (CDAI)

4.4.5.2.2. Secondary Outcomes:

- Achievement of Minimum Clinically Important Difference (MCID) (Curtis et al., 2015)⁵: (change in CDAI from baseline to follow-up = Δ CDAI)

| CDAI at Index | MCID to Define Improvement in Disease Activity at FU Visit If Δ CDAI>MCID |
|----------------------|---|
| | |
| Low: CDAI≤10 | 1 |
| Moderate: 10>CDAI≤22 | 6 |
| High>22 | 12 |

- Change in HAQ
- Change in patient pain
- Change in patient fatigue
- Number (%) of tofacitinib discontinuations prior to or at 6-month visit

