4.4.7. Analysis Plan

4.4.7.1. Aim 1: *Describe the characteristics of tofacitinib initiators with a history of rituximab exposure, at time of tofacitinib initiation*

Descriptive statistics for the variables listed in [Section 4.4.6](#) will be provided for all tofacitinib initiators with history of rituximab use. All variables will be measured at the index visit, as defined above. Categorical covariates will be described by frequency distribution while continuous covariates will be expressed in terms of their mean and standard deviation or median and interquartile range (IQR) as appropriate.

4.4.7.2. Aim 2: *Describe 6-month outcomes for tofacitinib initiators with a history of rituximab exposure*

Descriptive statistics for index visit characteristics will be provided for the subsets of patients included in this Aim (tfacitinib initiators who have a 6-month follow-up visit), as described in Aim 1.

Analyses of outcomes at the 6-month follow-up after tofacitinib initiation will be descriptive. Primary and secondary outcomes will be described as mean absolute differences for continuous measures and as frequencies and proportions for dichotomous measures, with corresponding 95% confidence intervals (95% CI). Mean absolute difference will be defined as the value at the 6-month follow-up visit minus the value at baseline. The number of patients that discontinue tofacitinib will also be summarized. A subgroup analysis related to the outcomes for Aim 2 will be carried out focused on patients who used rituximab immediately prior to tofacitinib.

All analyses will be conducted using Stata Release 16 (StataCorp LLC, College Station TX) and/or R Version 4.0.3 (The R Foundation for Statistical Computing, Vienna Austria).

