4.4.9. Sample Size and Power Considerations

As of the March 31, 2021 data cut, there were 390 tofacitinib initiators with any history of rituximab use. Of these,

- ~376 have baseline CDAI information
- Line of therapy (and baseline CDAI) is available for ~373, of whom n=8 (2%) are 3rd line and n=365 (98%) are 4th line
 - Note: since population is restricted to those with prior rituximab use, 3rd line use reflects patients with prior RTX use only.
 - 4th line reflects patients with one or more prior biologic in addition to RTX.
- ~107 have CDAI information at baseline and 6mo follow-up
- <10 patients have history of tuberculosis or history of lymphoma

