4.5.2. Limitations

The CorEvitas RA Registry used in this research includes a sample of adults with RA that are not necessarily representative of all adults with RA in the US, or of those in emerging markets outside the US. In particular, these are patients with RA with clinical visits with rheumatologists.

Most importantly for this study, in the US rituximab is typically prescribed as a later line therapy, after failure of one or more TNFi. It is also given as a first-line bDMARD to patients with contraindications to TNF inhibitors (e.g., interstitial lung disease) [1]. This may differ from prescribing patterns in countries other than the US, which could influence the generalizability of the results to RA patients outside of the United States.

In addition, history of medication use prior to enrollment is derived from what is reported by patients and their current rheumatologist within the registry. Since the registry is not based on an inception cohort, patients may not be able to recall their entire medication history, leading to possible mischaracterization regarding prior use of RTX. The registry captures physician-reported prescribing, but there are no measures of patient adherence. Confounding by indication can occur when factors that determine

physicians' selection of a particular treatment (e.g. disease severity, comorbidities) also affect the outcome being studied. There are certain conditions (TB, lymphoma) that would prompt the prescribing of rituximab. This population could have different outcomes than a population without these comorbidity histories.

Patients who maintain treatment at 6 months may have different outcomes compared to the outcomes those who discontinue or switch would have had, had they not discontinued/switched. This study takes steps to mitigate this potential bias by including values at follow-up for those who discontinue treatment and values at switch for those who switch, as described above.

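### SAP 4.3 promises evidence of effectiveness, but an uncontrolled before-after change cannot separate a drug effect from regression to the mean

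*SAP*

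**What the plan says.** SAP 4.3 (Expected Results) gives two purposes. One is to characterise the patients. The other reads: "The study will also provide evidence of the effectiveness of tofacitinib in the real world", in a population with rituximab experience. SAP 4.1 and Protocol section 7 name the intended users as healthcare providers in emerging markets.

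The design behind the second purpose is set out elsewhere in the SAP:

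- **Comparator (4.4.4):** there is none. "All patients in the study will be classified as exposed".
- **Estimate (4.4.7.2):** "Mean absolute difference will be defined as the value at the 6-month follow-up visit minus the value at baseline". It is reported "with corresponding 95% confidence intervals (95% CI"), and no adjustment is planned.
- **Expected direction (4.2.2.1):** there is no formal hypothesis, but "it is anticipated that outcomes will improve over the 6-month time period".
- **Size (4.4.9):** at the March 2021 data cut, about "107 have CDAI information at baseline and 6mo follow-up".

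The nearest limitation, in SAP 4.5.2 and Protocol 9.9, begins "Confounding by indication can occur when factors that determine" and concerns what drives the choice of treatment. The other limitations cover representativeness, recall of past medication, adherence, and discontinuation or switching. Neither section mentions regression to the mean, natural fluctuation or the absence of a comparator.

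**The concern.** Patients tend to start a new drug when their disease is more active than usual. If the baseline CDAI is partly a temporary peak, the next value will on average be lower whatever drug is given. A follow-up-minus-baseline difference adds that fall to any drug effect, and nothing in the analysis separates the two. The confidence interval measures sampling error only, so an interval wholly below zero shows that CDAI fell. It does not show why.

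MCID achievement has the same weakness. Tables 3 and 4 count improvers only, so the reader cannot set chance improvement against chance worsening.

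At stake is how the report will be read. A fall that the plan expects in advance, with an interval around it, could be passed to prescribers as evidence that the drug works after rituximab. The design cannot support that conclusion.

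**Working it through.** **No design figure to reproduce.** The documents state no power, effect size, SD or target precision. The counts they do give agree with each other: 8 + 365 = 373; 8/373 = 2.1% (stated 2%); 365/373 = 97.9% (stated 98%).

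**Inputs from the documents.** n = 107 with paired CDAI; a 95% interval; change = 6 months minus baseline; CDAI range 0–76; no minimum CDAI for entry (Protocol 9.2.1).

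**Assumed inputs.** CDAI SD 10–16 points; between-visit correlation ρ 0.5–0.9; shift (mean baseline minus the patients' usual mean) 0–10 points; drug effect zero.

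**Formulas**

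- Expected change from regression to the mean = −(1 − ρ) × shift
- SE = SD × √(2(1 − ρ)) / √107
- 95% CI = change ± 1.96 × SE
- Chance that the CI lies below zero = Φ(|change|/SE − 1.96)
- The expected CI excludes zero when shift/SD > 1.96 × √(2 / (107(1 − ρ)))

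The SE uses the same SD at both visits, which is an approximation under selection.

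**Shift needed at n = 107**

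| ρ | Expected CI excludes zero | 80% chance of exclusion |
|---|---|---|
| 0.5 | 0.38 SD | 0.54 SD |
| 0.7 | 0.49 SD | 0.70 SD |
| 0.8 | 0.60 SD | 0.86 SD |
| 0.9 | 0.85 SD | 1.21 SD |

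For ρ = 0.5: 1.96 × √(2/53.5) = 1.96 × 0.193 = 0.38. For ρ = 0.9: 1.96 × √(2/10.7) = 1.96 × 0.432 = 0.85. If the SD is 13, these are about 4.9 and 11.0 CDAI points.

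**On the CDAI scale, SD 13, zero drug effect**

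| ρ | Shift | Change | 95% CI | Chance CI is below 0 |
|---|---|---|---|---|
| 0.5 | 5 | −2.5 | −4.96 to −0.04 | 51% |
| 0.5 | 10 | −5.0 | −7.46 to −2.54 | 98% |
| 0.7 | 5 | −1.5 | −3.41 to 0.41 | 34% |
| 0.7 | 10 | −3.0 | −4.91 to −1.09 | 87% |
| 0.9 | 10 | −1.0 | −2.10 to 0.10 | 43% |

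With no shift the chance is 2.5%. Over the whole grid it runs from 2.5% to 99.9%.

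**Check by simulation.** This used CDAI bounded at 0–76, long-run mean 16, SD 13, selection on baseline CDAI and zero drug effect. At ρ = 0.7, strong selection raised mean baseline from 16.7 to 26.5 and gave a change of −3.09. The formula gives −0.3 × 9.8 = −2.9. The chance of an interval below zero was 99%, 91% and 46% at ρ = 0.5, 0.7 and 0.9. It fell to 95%, 76% and 34% when 30% of patients had baseline carried forward, which SAP 4.4.3.3 allows if the last visit before discontinuation is the baseline visit. With milder selection at ρ = 0.7 (mean baseline 20.7) the change was −1.29 and the chance 29%.

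In the same zero-effect runs, 16–24% of patients met the MCID at ρ = 0.7 and 6–14% at ρ = 0.9.

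**Effect of n.** The SAP plans a later data cut, so n may differ from 107. At n = 150 the required shift falls to 0.32–0.72 SD for ρ 0.5–0.9.

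**The case against.** A reader might infer something stronger: that regression to the mean would by itself produce an interval excluding zero, so the planned result would appear even if the drug did nothing. The documents do not support that, for these reasons:

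- They give no CDAI mean, SD, correlation or strength of selection, and the calculation goes either way over the assumed ranges.
- Entry requires that CDAI be measured, not that it be high.
- For starts between visits, baseline is an earlier visit up to four months before initiation (SAP 4.4.3.1), which weakens selection on a peak.
- Rituximab may be stopped for insurance, safety or patient preference as well as for efficacy (footnotes to SAP Tables 1 and 2).
- About 98% of patients with known line of therapy had another biologic besides rituximab. Their high activity may be persistent, which means a higher correlation and less regression.
- Baseline carried forward gives zero change.

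All of this stands, and it limits the size of the claim to what could happen.

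A second objection is that the plan already calls itself descriptive, attaches no test or success rule to the interval, and warns that the sample may not represent emerging markets. This also stands, and it means that no planned estimate is wrong. But the descriptive label does not withdraw the sentence in 4.3, and generalisability is a different problem from attributing the change to the drug. Nor does the limitation on confounding by indication cover the point. It concerns which patients receive a drug, while regression to the mean concerns when their baseline is taken.

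Finally, counting improvers is how the plan defines MCID achievement, so it is not an error, and the documents give no MCID for worsening. Any count of worsening must be labelled accordingly.

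**Conclusion.** The point holds in conditional form. SAP 4.3 claims a property that the design lacks: an uncontrolled before-after change in a single exposed cohort does not give evidence of effectiveness. This conclusion needs no numerical assumption.

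The size does need assumptions. At about 107 pairs and zero drug effect, the expected 95% CI excludes zero only if patients start more than roughly 0.38 SD (correlation 0.5) to 0.85 SD (correlation 0.9) above their usual CDAI. Selection on high activity is a reasonable inference for patients starting a new drug, but it is not stated and its strength is unknown. An interval below zero would therefore not distinguish a drug effect from regression to the mean, and whether regression alone would produce one cannot be settled from the documents.

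**What to change.** 1. In SAP 4.3, replace the sentence with: *The study will describe 6-month change in outcomes after tofacitinib initiation; without a comparator it does not estimate effectiveness.* Name regression to the mean and the lack of a comparator in SAP 4.5.2 and Protocol 9.9.
2. For patients with a registry visit before the baseline visit, report mean CDAI at that earlier visit beside baseline and 6-month CDAI, with the n. State that it is unavailable for patients who initiate at enrollment. A baseline well above the earlier value would make regression to the mean more plausible. It would not prove it, because the disease may truly have worsened.
3. Optionally, add to Tables 3 and 4 the number (%) whose CDAI rose by more than the same 1/6/12 thresholds. Label it a descriptive mirror count, not a validated MCID for worsening.

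The cost is wording in two documents, one or two table rows from data the registry already holds, and a more modest claim.
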